### 9.2 Setting

Approximately 8000 patients from different care settings (primary care and secondary care, different specialties) will be enrolled consecutively at a total of approximately 800 sites. It is estimated that each site will contribute 10 patients, although additional patients - subject to approval - may be considered. At each study site, the patients will be enrolled consecutively. Patients will be stratified for High and Very High Risk (per physicians' assessment) as well as for previously and newly treated patients. Sites will be required to complete a patient screening log of eligible patients for this disease registry at their treatment centers. This log will document

how patients came to be included or excluded from the study, in order to assess the representativeness of the study population. Minimal information will be recorded for all patients who are screened for study enrolment, but no patient-identifiable information should be recorded. Those patients who provide their informed consent will be enrolled into the study.

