**Study population:**

The study population consists of Very High Risk and High Risk dyslipidemic patients previously diagnosed and treated as well as newly treated patients receiving their first LMT. At baseline data collection point, baseline characteristics (LDL-C and other lipid parameters, CV risk assessment, concomitant diseases such as diabetes and congestive heart failure, certain HEOR variables) and relevant medical history (CV events such as myocardial infarction and stroke) will be documented.

In addition, for the previously diagnosed and treated patients, details on the lipid modifying treatment during the year before enrolment will be collected.

This information will be collected from the patients' chart from all dyslipidemia-related visits at which the patient has been seen by the physician, starting from date of diagnosis.

At the follow-up data collection point at 1 year ( $\pm$  2 months), available information on the patients' routine management between baseline and this data collection point, and efficacy and safety variables will be collected: LDL-C and the other lipid parameters, inflammatory status, overall CV risk scores (SMART and Framingham risk scores will be calculated centrally based on collected patient information), CV events such as myocardial infarction and stroke, diabetes related parameters, renal function parameters, and the lipid-modifying therapy. As an optional assessment, PRO questionnaires will be completed by the patient preferably in the physician's office.

Electronic data capture (EDC) will be used for the recording of the information.

As this is a non-interventional study, only data that is based on routine clinical practice will be documented. Treatment pattern and treatment initiation, continuation or changes are solely at the discretion of the physician and the patient. There will be no attempt to influence the prescribing patterns of any individual treating physician. All medication will be prescribed according to usual standard of care and will not be provided by the study sponsor. Participation in the study will in no way influence payment or reimbursement for any treatment received by patients during the study.

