### 9.3 Variables

#### Parameters recorded during the observation period:

*To be documented at baseline (if available):*

- Eligibility
- Demographic and sociodemographic variables
- Vital signs
- Medical history, including CVD risk status-related medical history:
  - CV risk assessment with or without utilization of risk score
  - history/diagnosis and current status of dyslipidemia
  - heterozygous familial hypercholesterolemia (HeFH)
  - documented ASCVD either clinical or unequivocal on imaging
- Concomitant diseases
- For diabetic patients
  - disease type and date of diagnosis
  - treatment
  - microvascular complications
- Current concomitant medication for CVD
- Previous / current dietary restrictions
- Previous / current use of lipid-modifying treatment
 

Previous / current use of lipid-modifying treatment including details of dose, dose modification, switching, combination therapy, drug intolerance, insufficient responsiveness, investigators and patients assessment on compliance

  - Statin(s)
  - Bile acid sequestrant(s)
  - Cholesterol absorption inhibitor (Ezetimibe)
  - PCSK9 inhibitor(s)
  - Nicotinic acid
  - Drug combinations
  - Bempedoic acid and/or bempedoic acid fixed dose combination with ezetimibe
  - Other
- Laboratory parameters
  - Lipid variables
    - LDL-C
    - HDL-C, non-HDL-C, TC, apoB, TG, Lp(a)
  - Diabetes-related parameters
    - fasting glucose
    - HbA1c
  - Inflammatory status
    - hsCRP
  - Renal function parameters (GFR, serum creatinine, blood urea nitrogen (BUN))
  - Other laboratory parameters (liver function, serum chemistry, hematology)
- HEOR parameters
  - Hospital admissions
  - Length of hospital stay
  - Number of days in ICU
  - Interventions
  - Other HEOR parameters

- Adherence to former and current treatment
- Patient reported outcomes (EQ-5D-5L, PAM-13)

*To be documented at 1-year follow-up (if available):*

- Vital signs
- CVD risk status:
  - CV risk assessment with or without utilization of risk score
  - history/diagnosis and current status of dyslipidemia
  - heterozygous familial hypercholesterolemia (HeFH)
  - documented ASCVD either clinical or unequivocal on imaging
- Concomitant diseases
- For diabetic patients
  - disease type and date of diagnosis
  - treatment
  - microvascular complications
- Current concomitant medication for CVD
- Previous / current dietary restrictions
- Previous / current use of lipid-modifying treatment
 

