## 9.5 Sample Size Calculation

As this registry is intended to collect data under real-life conditions and the statistical analysis will be performed in a purely explorative way, no primary parameter has been defined for the sample size calculation. On a pragmatic basis, data of approximately 8000 patients will be collected, whose data is to be documented both retrospectively and prospectively (over a period of 1 year). This sample size of 8000 patients will provide sufficient precision (measured by width of 95% confidence interval) for the rates of CV death, nonfatal MTI, nonfatal stroke, and coronary revascularization during one year follow up.

Assuming an absolute reduction of LDL-C across all treatment modalities in a real-life setting of 0.9 mmol/L, the sample size shall provide information for an expected change in the relative risk of major vascular events with an absolute precision of  $\pm 13\%$  (relative precision  $\pm 16\%$ ).

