## 9.7 Data Analysis

This section describes the most relevant parts of the statistical analyses planned for a NIS/registry. All statistical methodology will be described in detail in the Statistical Analysis Plan (SAP) which will be finalized at the latest prior to database lock. All variables collected in the CRFs and/or other recordings (if applicable) and all derived parameters will be used in the statistical analysis.

A report including descriptive statistics of all documented parameters will be generated also if required for each participating country. Details on the selection criteria used will be given in the SAP and in the statistical section of the report.

Referring to the primary objective, the statistical analysis will be performed in a purely explorative descriptive way according to DSE SOP R-440.

Data will be collected at the following data collection points

- baseline ,
- 1-year prospective follow-up

Following analysis sets will be used for analysis

- The All-Documented Patient Set (APS) consists of all patients with any eCRF documentation.
- The Baseline Analysis Set (BAS) consists of all eligible patients of the APS who provide adequate baseline information.
- The Full Analysis Set (FAS) consists of all patients from the BAS with available 1-year follow-up data.
- The Safety Set (SAF) includes all patients who received at least one dose of bempedoic acid and/or bempedoic acid fixed dose combination according to their documentation in the eCRF.

No primary endpoint was defined in this study. No formal statistical tests will be performed within the statistical analysis.

All statistical analyses will be performed in a purely exploratory descriptive way.

Binary, categorical, and ordinal parameters will be summarized by means of absolute and percentage numbers within the various categories (including 'missing data' as valid category at baseline).

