Numerical data will be summarised by means of standard statistics (i.e. number of available data, number of missing data, mean, standard deviation, minimum, median, maximum, lower and upper quartile). In addition, adequate graphs (e.g. bar charts, box-whisker plots) may be presented to summarize the results for some parameters. Analysis of changes in numerical parameters (as the differences in Score risk between baseline and 1-year follow up) will be done by paired Wilcoxon signed rank test and paired t-test if assumptions of parametric tests will be met. Comparison of these 1-year changes between subgroups will be done by Kruskal-Wallis test and ANOVA test if assumptions of parametric tests will be met. Also adjusted analyses for age, sex and country effects will be done. Time-to-event variables will be analyzed via a Cox proportional hazard regression model presenting hazard ratios and the corresponding 95% confidence intervals. Additionally, adjusted Cox model for age, sex and country effects will be presented. In addition, Kaplan-Meier curves will be presented for time-to-event variables. Two-sided 95% confidence intervals will be presented for important parameters, but should be interpreted in an exploratory descriptive way.

Depending on the variable(s) of interest, additional selection criteria for patients (e.g. subgroup analyses) considered in specific analyses may be used, if considered useful during the statistical

analysis. Details on the selection criteria used will be given in the Statistical Analysis Plan (SAP) and in the statistical section of the report.

The statistical analysis will be performed using SAS version 9.4 or higher

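### Section 9.7 states no allowance for sampling about 10 patients per site, so standard 95% CIs for overall means, proportions and mean 1-year changes would be too narrow if outcomes vary between sites within countries

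*Combined protocol and SAP*

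**What the plan says.** Section 9.2 (Setting) describes consecutive enrolment of about 8000 patients at about 800 sites. On the number per site it says "It is estimated that each site will contribute 10 patients", and then that "additional patients - subject to approval - may be considered", so sites may differ in size. The Participating Centers section names the countries, leaving only the Nordic set open, and has sites chosen to spread over regions and specialties.

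Section 9.7, repeated in the Section 4 summary, names paired t and Wilcoxon tests for 1-year changes, ANOVA and Kruskal-Wallis for comparing those changes between subgroups, and Cox models for times to event. On adjustment: "Also adjusted analyses for age, sex and country effects will be done". On uncertainty: "Two-sided 95% confidence intervals will be presented for important parameters", to be read as exploratory. Section 9.7 leaves full methodology to a SAP to be final by database lock; its text is not among the documents.

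Section 9.5 sets 8000 pragmatically and then describes the precision this gives for one-year event rates, "measured by width of 95% confidence interval". No site term, random effect, robust variance or design effect appears in Sections 9.5, 9.7 or 9.9. Section 9.9 discusses differences between countries and regions only.

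**The concern.** Patients of one site share physicians, prescribing habits and local laboratories. The documents themselves make within-site correlation plausible. Section 9.2 says: "Treatment pattern and treatment initiation, continuation or changes are solely at the discretion of the physician and the patient". Among the variables in Section 9.3 is "investigators and patients assessment on compliance", so the same investigator rates all patients of a site. Laboratory values come from each site's own records (Section 9.4), and examinations follow each physician's routine (Section 10.6).

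When such patients are analysed as independent, the variation between sites is left out of the standard error of an overall mean or proportion. The interval is then too short and covers less often than its label says. The fallback tests do not help, because Wilcoxon and Kruskal-Wallis also assume independent patients.

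At stake is how readers judge the precision of overall LDL-C levels, LDL-C changes and treatment proportions, if these are among the parameters given intervals.

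**Working it through.** **Inputs from the documents.** About 800 sites and 10 patients per site: 800 × 10 = 8000, which reproduces the stated size. Intervals are two-sided 95%. The named countries are 12 plus one to three Nordic countries, so 13 to 15.

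**Inputs assumed.** No ICC is given. I use 0.01, 0.05 and 0.10.

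**1. Levels and proportions, ICC read as within country.** Design effect DEFF = 1 + (m − 1) × ICC with m = 10. The interval should be √DEFF times as wide. Actual coverage of the standard interval is 2Φ(1.96/√DEFF) − 1.

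**2. Same ICC read as a total, half of it between countries.** With countries as fixed strata, the between-country half does not add to the variance of an overall estimate. The ratio of true to standard variance is 10 × ICC/2 + (1 − ICC).

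| ICC | Reading 1: DEFF; wider by; coverage | Reading 2: ratio; wider by; coverage |
|---|---|---|
| 0.01 | 1.09; 4%; 94.0% | 1.04; 2%; 94.5% |
| 0.05 | 1.45; 20%; 89.6% | 1.20; 10%; 92.6% |
| 0.10 | 1.90; 38%; 84.5% | 1.40; 18%; 90.2% |

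For a proportion of 50%, the standard half-width is 1.96 × √(0.25/8000) = 1.10 points. Under reading 1 it becomes 1.14, 1.32 or 1.51 points; under reading 2 it becomes 1.12, 1.20 or 1.30.

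**3. Does country adjustment repair it?** No. In a simulation (800 sites of 10, 14 countries assumed, 3% of variance between countries), coverage at within-country ICC 0.05 was 90.8% unadjusted and 90.3% country-adjusted. At 0.10 it was 84.7% and 84.3%.

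**4. Site size (reading 1).** With unequal sites (assumed coefficient of variation 0.5), DEFF = 1 + (1.25 × 10 − 1) × ICC = 1.115, 1.575, 2.15, so 6%, 25% and 47% wider. With 20% lost by follow-up (assumed; 8 per site), DEFF = 1.07, 1.35, 1.70, so 3%, 16% and 30% wider.

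**5. Mean 1-year change.** The ICC of the change applies: ICC(1 − rs) / [ICC(1 − rs) + (1 − ICC)(1 − rw)], where rs and rw are the baseline-to-follow-up correlations of site effects and of patients within site. With a stable site effect (assumed rs 0.9, rw 0.5) it is 0.002, 0.010 and 0.022, so 1%, 5% and 9% wider. If rs is also 0.5, it equals the ICC of the level and the full 4%, 20% and 38% apply.

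**6. One-year event rates.** Assume rates of 3% and 6% and a gamma site frailty with variance 0.1 to 0.5. The implied ICC is 0.0030 to 0.0148 at 3% and 0.0060 to 0.0291 at 6%. With DEFF = 1 + 9 × ICC, intervals should be 1% to 12% wider (coverage 94.7% to 91.9%). The half-width goes from 0.37 to 0.38–0.40 points at 3%, and from 0.52 to 0.53–0.58 at 6% (0.5204 × √1.262 = 0.58).

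**7. Cox results and within-site contrasts.** In simulation, false-positive rates were 4.0–4.5% for a factor balanced within sites and 4.3–5.4% for a within-site factor in a Cox model, so they stay near 5%.

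**8. Choice of remedy.** Under reading 2, clustering by site without country strata makes intervals too wide by √(1.09/1.04) − 1 = 2%, √(1.45/1.20) − 1 = 10% and √(1.90/1.40) − 1 = 17%. In simulation (15 fixed countries assumed) at ICC 0.05 and 0.10, coverage was 92.5% and 90.1% for standard intervals, 97.1% and 97.7% with unstratified clustering, and 94.9% and 95.2% with clustering by site within country.

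**The case against.** - **The SAP may deal with it.** This stands as a limit on the claim. A reader might infer that the plan excludes a site-level method. The documents do not support that: Section 9.7 is silent, and the SAP it defers to is not available. Still, 9.7 is presented as the most relevant part of the analysis, and it lists adjustment factors without site.
- **Countries are fixed strata.** This stands. A reader might infer that any positive within-site correlation shortens the intervals by the full design effect. Only the part within countries does so for an overall estimate, which is why two readings of the ICC are shown and the remedy must be stratified.
- **The affected intervals may not be planned.** This stands in part. The descriptive summaries in 9.7 list no intervals, and its important parameters are not defined. That these include LDL-C levels, changes or treatment proportions is plausible but inferred. Country figures are offered only if required, and no comparison by specialty or care setting is planned.
- **The sample size does not depend on interval width.** This stands. A reader might infer from Section 9.5 that width justified 8000. The number was set pragmatically, and width only describes what it delivers.
- **The study is exploratory, with no primary endpoint.** This limits the consequence but does not correct an interval labelled 95%.

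**Conclusion.** The point holds as a conditional one. Where 95% intervals for overall means, proportions or mean 1-year changes are computed in standard form, and outcomes vary between sites within a country, they will be too narrow. Country adjustment does not cure this.

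The size rests wholly on assumed ICCs. At 0.01 it is minor. At 0.05 to 0.10, intervals for levels and proportions should be 20% to 38% wider if the ICC is within country, or 10% to 18% if half of it lies between countries. Event rates, and changes where site effects are stable, are affected less. It would go too far to say that every interval in the plan is affected: the hazard ratios and contrasts balanced within sites are nearly unharmed.

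In absolute terms the intervals stay short with 8000 patients, and no decision in the plan depends on them. This is an improvement worth considering, not a flaw that threatens the study.

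**What to change.** Add to Section 9.7 or the SAP:

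> 95% CIs for means, proportions and mean 1-year changes, and for any country-level estimate or comparison of site-level factors that is reported, will use variance clustered by site with country as stratum, with a t reference based on the number of sites minus the number of countries. Observed within-country site ICCs will be reported for LDL-C, 1-year LDL-C change and the main treatment proportions.

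In Section 9.5, state whether the quoted precision assumes independent patients. Clustered variance for Cox models and within-site contrasts is optional.

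The cost is two sentences in 9.7 or the SAP and one in 9.5. Standard procedures in the SAS version already planned suffice, and no new data are needed. The drawbacks are somewhat wider intervals, a little more analysis work, and a less reliable variance in countries with few sites. If the observed ICCs prove negligible, the intervals will hardly change.

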### **9.8 Quality Control/Monitoring**

Data quality checks will be performed on an ongoing regular basis. Queries will be raised by the responsible CRO and shall be answered by the site in due course. The purpose is to ensure that the rights of the patients are protected, that the reported data are accurate and complete, and that the conduct of the study is in compliance with the observational plan and applicable regulatory requirements.

Particular attention will be paid during monitoring activities to the completeness and correctness of safety data.

The physician will comply with the confidentiality policy as described in the site contract. The physician will comply with the observational plan and the requirements described in the contract. The physician is ultimately responsible for the conduct of all aspects of the NIS at the site and verifies by signature the integrity of all data transmitted to the sponsor.

On-site monitoring will be performed in 20% randomly selected sites. During on-site monitoring the monitor will verify 100% of informed consent documentation and perform source data verification against the patients' medical records in randomly selected patients (3 per site).

This study will be conducted according to the rules of 'Good Pharmacoepidemiology Practice' (GPP) and the 'Guideline on Good Pharmacovigilance Practices' (GVP). Related quality control mechanisms (e.g., data plausibility checks, monitoring of data) will be performed accordingly.

### **9.9 Limitations of the Research Methods**

Although sites will be selected to guarantee representativeness for the respective country or region as much as possible, sites also need to have sufficient capabilities, interest and capacities to participate in the NIS. This may influence the sites' representativeness in some smaller regions.

Eligible patients not giving their informed consent to participate in the NIS cannot be enrolled. Therefore this may impact the consecutive enrolment at a site. To be able to assess the consecutiveness of enrolment, eligible patients will be listed in the patient screening log. Patients participating in competing interventional trials are not eligible and will not be entered in the screening list.

At the annual documentation time point all relevant changes/events since the last documentation time point need to be entered. Due to the long time between Baseline and the Follow-up data collection point an underreporting of data might occur that are not considered essential or that are difficult to remember. The patient memory aid and the patients' medical records at the site shall support the precise documentation of the time between two annual data documentation time points. The utility of both records is however influenced by the precision and accuracy with which the memory aid and the medical records have been completed in the meantime. It is expected that possible underreporting will not appear in case of severe events and hospitalizations and that this data is considered to be representative for the whole study population.

In addition to the above mentioned underreporting of events, the time between two documentation points might cause an incorrect documentation of treatment changes. This could lead to a misclassification with respect to the exposure. However, this risk is considered to be low as relevant treatment changes are usually documented in the medical records and can furthermore be entered into the eCRF at any time (log-file approach). In addition, the patient memory aid again supports a precise documentation.

Also differences between the countries/regions might occur, especially when rating compliance. Therefore, especially for the compliance the analysis by country/region will be carefully looked at. In case that there will be mentionable differences, the interpretation has to be very careful and should consider regional differences.

As the study is non-interventional, only data from the clinical routine treatment can be obtained. Therefore some information may be missing or unavailable. This needs to be taken into account when data are analyzed and reported.

No explicit non-eligibility criteria are defined to avoid selection of patients and thus violation of the 'real-life' principle.

## 10 PROTECTION OF HUMAN SUBJECTS

### 10.1 Review by Ethics Committees/Competent Authorities

Notification to or approval by independent Ethics Committees (IECs) and competent authorities (CAs) or other organizations will be performed as required by national regulations in the participating countries before commencement of enrolment at a study center.

